# 3.2 Primary Study Endpoints

Due to the pilot phase design of this clinical trial, it is not feasible to designate primary study endpoints. With this in mind, we do consider the voluntary movement assessments, gait analysis, and functional mobility tests to be the primary sets of endpoints used to quantify ES-related datasets associated with addressing the specific aims of this proposal.

# **Secondary Study Endpoints**

Secondary endpoints include spasticity and MS Quality of Life Inventory.

		Pre/ No Stim	Stimulation + Task-specific Training			Post/ Stim ON and OFF	
Outcomes	Specific Measure	wk 0	wk 1	wk 2	wk 3	wk 4	wk 4/5
	Primary						
Gait Analysis	EMG, Kinematics, Kinetics	Χ					X
Voluntary Movement	EMG, Kinematics	X	X			X	X
Spasticity	MAS, Pendulum Test	Х					X
Secondary							
Functinal Mobility	TUG	X					X
MS Quality of Life Inventory	MSQLI	X					X

# 3.3 Primary Safety Endpoints

Primary safety endpoints of the study will be oriented to adverse events that could originate from the implantation of the ES electrodes, or the operation of the neurostimulator device as well as to those that could arise from performing the task-specific training sessions. Participants will be asked to report any discomfort that they encounter throughout the study. A detailed selection of the candidates by the Principal Investigators and the study team will be crucial to select individuals who fit the inclusion criteria of the study, minimizing risk for

34-36

potential adverse events throughout the study. Subjects will undergo a screening phase oriented to identify conditions that could potentially represent a higher than the expected risk for conducting this study.

To visualize electrode positioning of the ES device, X-ray imaging will be performed. To limit adverse events that could result from operating the device, stimulation parameters will be selected within safe ranges as provided by the manufacturer.

#### Subject Selection, Enrollment and Withdrawal 4 Year 1 Year 2 Year 3 Month 1-3 4-6 7-9 10-12 16-18 19-21 13-15 22-24 25-27 28-30 31-33 Subject 1 Screening and baseline visit Subject 2 Stim + task-specific training, Subject 3 post-visit Subject 4 Subject 5 Subject 6 Subject 7 Subject 8 Subject 9 Subject 10

Data Analysis, Interpretation, Documentation

Ten subjects with a diagnosis of Progressive MS (EDSS 6.5) will be enrolled. Subjects will be selected based on the following criteria:

#### 4.1 **Inclusion** Criteria

- Myelopathy secondary to Progressive MS
- No clinical or radiologic MS relapses for > 5 years
- EDSS score of 6.5 (constant bilateral assistance required to walk about 20 meters without resting) as assessed by a Neurologist with a specialty in MS
- Able to ambulate 10 feet independently with or without gait aid use
- At least 21 years of age
- No changes to spasticity medications or dalfampridine over the last 3 months

#### 4.2 **Exclusion Criteria**

- Currently a prison inmate, or awaiting trial, related to criminal activity
- Pregnancy at the time of enrollment
- History of chronic and/or treatment resistant urinary tract infection
- Spasticity (grade of 4) measured bilaterally in two muscle groups using Modified Ashworth Scale (MAS). Muscle groups tested will include bilateral knee flexors, extensors; ankle plantarflexors, dorsiflexors
- Unhealed decubitus ulcer
- Unhealed skeletal fracture
- Receiving diathermy treatment
- Active participation in an interventional clinical trial

- Any illness or condition which, based on the research team's assessment, will compromise the patient's ability to comply with the protocol, patient safety, or the validity of the data collected during this study.
- History of coagulopathy or other significant cardiac or medical risk factors for surgery
- Ventilator-dependent respiration
- Diagnosed with cardiopulmonary dysfunction (e.g., chronic obstructive pulmonary disease, cardiac failure, or heart arrhythmia)
- Untreated clinical diagnosis of depression
- History of frequent hypotension characterized by light headedness, or loss of consciousness
- History of frequent hypertension characterized by headache, or bradycardia
- Any active, implanted medical device
- Treatment of chemodenervation and/or neurolysis during the trial, or within 6 months of initiating the trial

# 4.3 Subject Recruitment, Enrollment and Screening

We will initially recruit participants from existing resources including individuals who have expressed interest in clinical research through the Mayo Clinic Multiple Sclerosis Clinic, Mayo Clinic volunteer research participant database, Mayo Clinic clinical trials website, Mayo Clinic electronic medical record, and ClinicalTrials.gov. The Mayo Clinic Center for Multiple Sclerosis and Autoimmune Neurology (CMSAN) has prospectively enrolled over 1000 patients with MS in an observational biorepository study. These patients are consented for further contact to discuss enrolment in clinical trials, such as the proposed study. In addition, a subspeciality MS clinic is run daily, 52 weeks per year. Patients are seen by neurology, physiatry, urology, ophthalmology, and neuropsychology. Mayo Clinic's prior research in progressive MS, particularly in remyelinating therapies has resulted in a continuous stream of solicitations from candidates interested in therapy for progressive MS. The rate of up to four subjects enrolled annually will be easily achievable. We have successfully recruited individuals with similar inclusion/exclusion criteria as the proposed work, and we have had very successful recruitment, retention, and compliance.

Prior to participating in the screening phase, a member of the research team will provide an explanation of the study and answer questions asked by the potential study participant.

Participants will be given sufficient time to make an informed decision, review relevant informed consent documents, and ask questions. Once questions and concerns have been addressed to the potential subject's satisfaction, the informed consent form will be signed and dated by the participant and the PI. A copy of the signed consent documents will be provided to the subject. Following informed consent, screening tests will be performed. A final decision on study participation will be made by the PI and study team.

# 4.4 Early Withdrawal of Subjects

Subjects will be informed that they have the right to withdraw from the study at any time. Similarly, the PI has the authority to withdraw the subject from the study at any time.

# 4.4.1 When and How to Withdraw Subjects

Factors that may lead to withdrawal:

- Study subject health concerns
- Protocol violation (e.g., non-compliance)
- Study-related serious adverse events
- Study subject's decision to pursue activities outside of the study protocol, that in the opinion of the PI, may compromise data collected within the study protocol
- The emergence of other problems, events, or information, that may adversely affect the rights, safety, or welfare of the study subject, or may substantially compromise data collected within the study protocol

If a serious adverse event occurs during an activity described in this protocol, a consensual decision will be made between the study subject and the PI regarding withdrawal from the study.

In the event of study withdrawal, the ES electrodes will be explanated. If explanation surgery is urgent due to concern for the subject's health, the cost of the explanation procedure will be covered by the research study. Aside from standard recovery, no adverse effects are anticipated from the removal of percutaneous electrical stimulator.

If a subject fails to attend protocol activities and fails to respond for follow-up, a communication attempt will be made to determine if non-compliance is related to an adverse event.

# 4.4.2 Data Collection and Follow-up for Withdrawn Subjects

If a subject withdraws or is withdrawn from the study for any reason before study completion, an attempt will be made to carry out an exit interview. The reason for withdrawal will be documented by the research team.

# 5 Study Device

# 5.1 Description

# Epidural spinal cord stimulator (Model 3086, Abbott Neuromodulation; Nomad, Ripple Neuro)

The ES electrode lead is an implantable neurostimulation device that is FDA-approved for treatment of neuropathic pain disorders. Up to two ES electrode leads will be implanted temporarily along the dorsal epidural surface of the lumbosacral enlargement (i.e., L2-S1 spinal segments). The externalized ends of the ES electrode leads will be connected to the Nomad neurostimulation system to deliver electrical pulse waveforms to the epidural surface.

# 5.2 Method for Assigning Subjects to Treatment Groups

Subjects will be all receive ES combined with task-specific training.

# 5.3 Preparation and Administration/Implantation of Investigational Device

[figure not shown]
Description of ES system implantation/administration

We recently published a detailed explanation of the procedure to implant a permanent

electrode array connected to an implanted pulse generator, along with a detailed description of the electrophysiological approach used to guide electrode positioning over the lumbosacral enlargement in humans with SCI (Calvert, 2018). The same approach will be used during this study to guide electrode placement via electrophysiological monitoring of spinal motor evoked potentials.

The procedures for percutaneously implanting Abbott ES electrodes are performed daily at Mayo Clinic to treat patients suffering from neuropathic pain. Prior to implantation, subjects will undergo a pre-operative evaluation to minimize the risk of unexpected complications. Pre-operative assessments may be performed to check for any signs of infection.

To implant the temporary spinal electrodes, under fluoroscopy an electrode insertion needle will be placed into the epidural space using a paramedian approach and loss of resistance technique to advance through the ligamentum flavum, followed by fluoroscopic visualization of the needle's position. Once positioning is confirmed, the needle stylet will be removed, and the needle will be advancedinto the epidural space.

Then, the leads are advanced in an anterograde fashion to the level of the lumbosacral enlargement utilizing fluoroscopic guidance. Following electrophysiologic confirmation of electrode positioning, the needle and stylet will be removed, the implantation site will be dressed, and the leads will be secured to the skin via an adhesive bandage. The implantation site will be monitored for signs of infection, tissue erosion, or dislodged lead wires. One day post implantation, the first follow up will take place to evaluate for adverse events. Trained

Page 16 of 33 [name]. team members will monitor the percutaneous site on an ongoing basis during training session to ensure the site remains intact and sterile. Study team members have received training from a registered nurse within the pain specialty program at Mayo Clinic.

#### Procedure to explant ES electrode leads

After completing task-specific training with ES, the adhesive bandage covering the implantation site will be removed, the incision site will be opened, and the leads will be carefully retracted. Finally, the incision site will be cleaned and dressed.

If complications associated with temporary lead implantation (e.g., infection, severe lead migration, device malfunction, etc.) are observed, the PI will make an informed decision whether to perform explantation prior to completion of task-specific training. Participants will be followed up within 5 days of explantation for adverse events. They will be provided information for monitoring the site remotely as well.

# 5.4 Subject Compliance Monitoring

Throughout the study, research staff will monitor study protocol compliance. This will include review and verification of all protocol-related procedures and records. The PI will oversee compliance and determine the appropriate response to non-compliance events.

# 5.5 **Prior and Concomitant Therapy**

A subject's prior therapy regimen will not impact the PI's decision regarding enrollment into the study. If the subject fits the inclusion criteria and does not demonstrate any exclusion criteria characteristics, prior exercise or therapy programs will not exclude their participation in the study. While enrolled in the study, subjects will be asked to follow the instructions from the study staff regarding concurrent activities. For example, if the study subject performed locomotor training at a local gym prior to the study, they would be asked to continue that activity while participating in the trial.

# 5.6 Packaging and Labeling

The packaging of the devices will be from the manufacturer's clinical supply. The following will be added to the devices used within this investigation:

"CAUTION – Investigational Device. Limited by Federal (or United States) law to investigational use"

# 5.7 Masking/Blinding of Study

This is an unblinded study. The PIs, co-investigators, and subjects will not be blinded, and allparticipants will receive the same treatment.

# 5.8 Receiving, Storage, Distribution and Return

# 5.8.1 Receipt of Investigational Devices

The percutaneously-delivered ES electrode leads will be acquired either through purchase or donation from Abbott. A representative from Abbott will ship the devices to Mayo Clinic and will be properly inventoried prior to the scheduled date of surgical implantation.

The Nomad neurostimulation system has been purchased from Ripple Neuro, shipped to Mayo Clinic, and inventoried within the ART Lab.

Any product discrepancies or damage will be documented in the study files and the supplier will be notified. Then, appropriate action will be taken by the PI to fully address the issue.

# 5.8.2 Storage

ES electrode leads will be stored within a secured surgical materials area at Mayo Clinic. Access to this area is granted solely to Mayo Clinic staff involved in surgical implantation procedures.

The Ripple Nomad system will be stored in the ART Lab, which is a secured area that can only be accessed by ART Lab staff.

# 5.8.3 Distribution of Study Device

In accordance with Mayo Clinic policy, the brand, model, date of implantation, and date of explantation of all ES electrode leads will be recorded in the Surgical Inventory Management System. This information will be made available within the electronic medical record of each subject. Additionally, a copy of this information will be stored within each subject's case file.

# 5.8.4 Return or Destruction of Study Device

At routine intervals and at the completion of the study, there will be a reconciliation of devices shipped, devices utilized, and devices remaining. This reconciliation will be logged on the Device Accountability form, signed and dated. Any discrepancies noted will be documented, the PI will be notified, and an investigation will be conducted to determine thecause of the discrepancy.

# 6 Study Procedures

# 6.1 Screening

Subjects will complete a variety of assessments and procedures to determine their enrollment eligibility. When possible, eligible subjects will have their screening data used as baseline data collection. The following tests/activities will be performed to determine eligibility based on the inclusion/exclusion criteria listed in this document.

- Review of available medical records
- Neurology and Physical Medicine and Rehabilitation clinical exams
- EDSS score evaluation
- Pregnancy test
- Spasticity examination
- Evaluation of rehabilitation task ability and range of motion of impaired joints
- Spine MRI
- Body weight

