# 3 Study Design

# 3.1 General Design

This is a pilot study that will include a total of 10 subjects with Progressive MS (EDSS 6.5). All subjects will complete 1 month of ES and task-specific training. Expected duration of subject participation is less than 2 months. Baseline assessments will be obtained prior to implantation and post-stimulation assessments will be obtained prior to explantation, with stimulation on and off.

SCREENING	BASELINE	STIMULATION	POST- STIMULATION	
	Baseline Assessments	Minimum 12 Sessions	End Assessments	
Assessment of Inclusion/Exclusion criteria by study team	Clinical, Electromyography, Movement Assessments& Surveys	Stimulation + Task- Specific Training	Clinical, Electromyography, Movement Assessments & Surveys	STUDY END
	No Stim	Percutaneous Stimulation	Stim on/Stim off	
l-month pre- enrollment	Week 0-1	Weeks 1-4	Week 4-5	

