#### **Outcome Measures** 6.4

The following outcome measures will be collected with tests occurring over an approximately one-week period of time for each time point. Photographic and video images will be recorded throughout the study but will not be shown to anyone outside the study team without the subject's written consent.

		Pre/ No Stim	Stimulation + Task-specific Training			Post/ Stim ON and OFF	
Outcomes	Specific Measure	wk 0	wk 1	wk 2	wk 3	wk 4	wk 4/5
	Primary						
Gait Analysis	EMG, Kinematics, Kinetics	Χ					X
Voluntary Movement	EMG, Kinematics	Χ	Χ			Χ	X
Spasticity	MAS, Pendulum Test	Χ					Χ
Secondary							
Functinal Mobility	TUG	Χ					X
MS Quality of Life Inventory	MSQLI	Χ					X

Aim 1 will quantify the effect of ES and task-specific training on lower extremity motor function in individuals with severe lower extremity motor disability due to progressive MS using the primary outcomes of kinematics (movement), kinetics (forces), and electromyography (muscle activity, EMG) collected during gait, standing, and side lying motor tasks. Data will be reduced and summarized using standard biomechanical approaches, to quantify gait rhythm, lower extremity joint and body center of mass ranges of motion (during gait, standing, and side lying), and timing of muscle activations and ground reaction force peaks. Secondary outcomes include functional mobility assessments utilizing motion capture data, as well as the Timed Up and Go (TUG) test. Safety and tolerability will be assessed while monitoring vital signs and stimulation responsiveness during daily sessions and testing dates.

Aim 2 will determine the impact of ES and task-specific training on non-motor spinal related dysfunction in individuals with severe lower extremity motor disability due to progressive MS using the primary outcomes of the qualitative pendulum test (Smith et al., 2000) and the Modified Ashworth Scale to describe spasticity levels. Secondary outcomes will include the MS Quality of Life inventory that includes questions about bowel, bladder and sexual function, quality of life and pain, among others.

Aim 3 will be an *exploratory aim* to collect electrophysiological and biomarker data that may help us gain a mechanistic understanding of findings in Aims 1 and 2. To assess the Page 20 of 33 [name].

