*Spasticity:* One or both of the following will be used to measure lower extremity spasticity: the Modified Ashworth Scale (MAS) (Bohannon et al., 1987) where the subject will be placed in a supine position and flexor and extensor muscles are assessed according to the MAS protocol; and the pendulum test which is a biomechanical method of evaluating muscle tone using surface-based kinematic assessments that uses gravity to provoke muscle stretch reflexes during passive swinging of the lower limb.

*Functional mobility test:* The following test will be performed: Timed Up and Go (TUG) (Podsiadlo et al., 1991). The TUG test is used to assess a person's mobility and requires both static and dynamic balance.

*MS QOL Inventory (MSQLI):* Multiple Sclerosis Quality of Life Inventory (Fischer et al., 1999), a comprehensive outcomes assessment battery will be administered to assess many facets of the participants' quality of life. Several scores, are captured, including Overall Health Status, Modified Fatigue Scale, Sexual Satisfaction Scale, Bladder Control Scale, Bowel Control Scale, Perceived Deficits Questionnaire and Mental Health Inventory.

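### Section 6.1 lets the screening Modified Ashworth reading, which also decides eligibility, replace the scheduled week-0 baseline in some participants and not others

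*Combined protocol and SAP*

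**What the plan says.** Section 6.1 closes its introduction with the rule "When possible, eligible subjects will have their screening data used as baseline data collection". The list that follows includes a "Spasticity examination" and an "Evaluation of rehabilitation task ability and range of motion of impaired joints", together with the EDSS, spine MRI, body weight and other eligibility checks.

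The rest of the protocol treats baseline as a separate occasion. The Section 3.1 schematic has one column for screening, in the month before enrolment, and another for baseline, at week 0-1. The outcome tables in Sections 3.2 and 6.4 both schedule spasticity (MAS and pendulum test) at week 0. Section 6.4 describes "tests occurring over an approximately one-week period of time for each time point".

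Section 4.2 excludes candidates with MAS grade 4 on both sides in two muscle groups. Both outcome tables list spasticity as primary, and Aim 2 in Section 6.4 names MAS as a primary outcome. The text under Secondary Study Endpoints calls spasticity secondary. On the choice of measure, Section 6.4 says "One or both of the following will be used to measure lower extremity spasticity".

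Section 7.1 makes participants their own controls. Section 7.2 uses the baseline measure as a regression covariate and reports SDs of pre-post differences and pre-post correlations to help size future studies. Section 7 does not say which pre-treatment value is analysed.

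**The concern.** There is no control arm, so the pre-treatment value is the comparator for any pre-to-post statement about spasticity. Two things go wrong if that value is sometimes the screening MAS.

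First, the reading was used for selection. An exclusion rule that removes high scores keeps some people whose reading happened to be low that day. On average their next reading is higher with no change in the underlying condition, and nothing in a single-arm design cancels that shift.

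Second, the age of the baseline would differ between participants according to what was feasible. The SD of change and the pre-post correlation would then describe a mixture of intervals, and a future trial with a fixed interval could not use them cleanly. Supplying such estimates is a stated purpose of the modelling in Section 7.2.

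**Working it through.** The plan has no figure to reproduce. Section 7.1 reports no power calculation, and the documents give no SD, reliability, correlation or exclusion rate for MAS. Steps 3 and 4 therefore rest on assumed ranges.

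**Step 1. Which outcomes can be affected**

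| Outcome (Section 6.4) | Scheduled at week 0 | On the Section 6.1 screening list |
|---|---|---|
| Gait: EMG, kinematics, kinetics | yes | no |
| Voluntary movement: EMG, kinematics | yes | not named; the task-ability and range-of-motion item is unclear |
| MAS | yes | yes, through the spasticity examination and the Section 4.2 exclusion |
| Pendulum test | yes | not named |
| TUG | yes | not named; same unclear item |
| MSQLI | yes | no |

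Only MAS clearly overlaps.

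**Step 2. Pre-to-post interval**

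Inputs from Section 3.1: baseline at week 0-1, post-stimulation at week 4-5, screening up to one month (about 4.3 weeks) earlier.
- Week-0 baseline: 4 - 1 = 3 weeks to 5 - 0 = 5 weeks.
- Reused screening value: up to 5 + 4.3 = 9.3, about 9 weeks.

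**Step 3. Selection artefact when the screening MAS is reused**

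Treat the score as normal, exclude the top fraction f, and let a later reading correlate ρ with the screening reading. With no treatment effect, expected change = (1 - ρ) × φ(c)/(1 - f), where c is the normal quantile at 1 - f. Results are in SD units; a positive sign means worse spasticity.

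| f (assumed) | φ(c)/(1 - f) | ρ = 0.5 | ρ = 0.7 | ρ = 0.9 |
|---|---|---|---|---|
| 2% | 0.049 | 0.025 | 0.015 | 0.005 |
| 5% | 0.109 | 0.054 | 0.033 | 0.011 |
| 10% | 0.195 | 0.097 | 0.058 | 0.019 |
| 20% | 0.350 | 0.175 | 0.105 | 0.035 |

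A simulation at f = 10% gave 0.097, 0.059 and 0.020 with reuse. With a separate week-0 reading it gave 0.001, 0.001 and 0.000, so a fresh reading removes the artefact.

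For scale, the standard error of a mean change in ten people is √(2(1 - ρ)/10): 0.316 SD at ρ = 0.5 and 0.141 SD at ρ = 0.9. The largest drift is 0.175/0.316 = 0.55 of one standard error.

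**Step 4. SD of the pre-post difference**

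For one interval, SD of difference = √(2(1 - r)) in SD units. If m of ten participants reuse the older value, the variance is 2(1 - r₁)(10 - m)/10 + 2(1 - r₂)m/10, with r₁ the correlation for the week-0 value and r₂ that for the screening value. Take r₁ = 0.8 and r₂ = 0.7 (assumptions).
- m = 0: √0.40 = 0.632.
- m = 5: √(0.20 + 0.30) = √0.50 = 0.707. Ratio 0.707/0.632 = 1.12; future sample size 0.50/0.40 = 1.25-fold.
- m = 10: √0.60 = 0.775. Ratio 1.22; future sample size 1.5-fold.

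A larger fall, from 0.8 to 0.6, or a fall from 0.9 to 0.8, gives 1.5-fold with five reused and 2.0-fold with all ten.

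**The case against.** The best defence is that the sentence does little harm. Most outcomes are not collected at screening, so they can only come from week 0. Section 4.1 requires more than five years without relapse and three months without a change in spasticity medication or dalfampridine, and Section 1.1 describes slow worsening. A MAS value a month old may therefore be nearly as good as a fresh one. The exclusion rule needs grade 4 bilaterally in two muscle groups, among people who must also be able to walk 10 feet, so few candidates may be removed. A truncated normal is only a rough model for an ordinal rule covering several muscles. The pendulum test may be the spasticity measure used, and it plays no part in eligibility. Reusing EDSS, MRI or body weight spares participants a repeat.

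Most of this stands, and it limits the point to MAS and to a modest size. It also rules out four broader readings:
- That all pre-treatment values are taken at mixed times. The screening list does not support this beyond MAS.
- That every comparison is compromised. The stimulation-on versus stimulation-off contrast at the end of treatment (Section 3.1) uses no baseline.
- That 22% is the inflation from mixed timing. That figure needs all ten values reused, in which case the source is no longer mixed; with five reused it is 12%.
- That Section 6.1 contradicts the Section 3.1 statement "Baseline assessments will be obtained prior to implantation". A screening value also precedes implantation. The conflict is with the separate week 0-1 column, the week-0 MAS entry and the window of about one week.

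The defence does not supply a rule. Nothing elsewhere says which MAS value is analysed or how old it may be.

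**Conclusion.** The point holds for MAS. Followed as written, Section 6.1 can replace a scheduled week-0 reading of an outcome listed as primary with an older reading that also decided eligibility, in some participants and not others.

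The consequences are modest. The drift of 0.005 to 0.175 SD depends on the assumed 2-20% excluded and reliability of 0.5-0.9. A reader might infer that regression to the mean could produce a false benefit. It would not here, because the rule removes high scores and the drift is towards worse spasticity. The effect on planning figures is potentially the larger one: about 12% on the SD of change, or a 1.25-fold sample size, if half the values are reused and the correlation falls from 0.8 to 0.7. The documents give no evidence on whether it would fall, and if a month makes no difference this part vanishes. This does not threaten the study's validity; correcting it is a cheap improvement.

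**What to change.** In Section 6.1, limit the reuse of screening data to items that are not outcome measures, such as EDSS, MRI and body weight. State that the screening MAS serves eligibility only and that the analysed MAS baseline is taken at the week-0 assessment in every participant, as Sections 3.2 and 6.4 already schedule. Say in Section 7.2 that this is the baseline used in the regression, the differences and the correlations, and record its date. Wording the limit by outcome measure also settles the unclear task-ability and range-of-motion item.

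The cost is a text change and a few minutes of participant and staff time to repeat MAS at a visit that takes place anyway. A weaker alternative is to keep reuse but set a maximum age and record the date and source of each value. That limits the mixed timing but leaves the eligibility reading as the baseline.
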